#### STUDY PROTOCOL

#### Study Design

The trial was conducted between 01AUG 2016 and 25FEB 2020 at 6 clinical sites: five University academic medical sites and one University active-duty military hospital. The trial consisted of ten-week, randomized, double-blind, placebo-controlled administration of losartan or placebo. Eligible participants were randomized in a 1:1 ratio based on a randomly permuted block design stratified by site. Participants were prescribed 25 mg of active drug or placebo at Week 0 and then flexibly uptitrated (as tolerated) to 50 mg by Week 2, 75 mg by Week 4, and then 100 mg at Week 6. If significant side effects were encountered, the dosage could be held or reduced to a minimum of 25 mg and held stable at Week 6. Participants unable to tolerate the 25 mg dose were withdrawn from the study.

Losartan and placebo were prescribed as identical capsules, with the losartan overencapsulated. Randomization lists were prepared by the biostatistics analytical team (led by SJ) and distributed to research pharmacies at the sites who dispensed the drug. Only the biostatistics team had access to the treatment assignment codes.

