#### Study Participants

Potential subjects participated in informed consent procedures approved by Institutional Review Boards for each performance site and the Department of Defense Human Research Protection Office (HRPO). A Data Safety Monitoring Board (DSMB) oversaw safety and progress of the study. To be included in the trial, veteran or civilian women and men, aged 18-70 years were required to meet past-month criteria for posttraumatic stress disorder (PTSD) according to DSM-5. Participants were required to have a CAPS-5 score of  $\geq$  25 at screening in order to enter the trial.

Exclusion criteria were: 1) current, imminent risk of suicide (as assessed by the C-SSRS (23)), 2) active psychosis, 3) moderate or severe DSM-5 alcohol or other substance use disorder in the past 3 months, 4) unable to attend regular appointments, 5) prior intolerance of or allergy to losartan or other ARBs, 6) medical illness likely to result in imminent hospitalization or for which treatments are contraindicated (based on lab results, medical history and physical exam) (e.g., systolic blood pressure < 90 mm Hg), 7) serious cognitive impairment (as evidenced by cognitive impairment felt likely to interfere with the ability to participate meaningfully in the study); traumatic brain injury was not excluded unless there was serious cognitive impairment, 8) concurrent ACE Inhibitors or ARBs, 9) concurrent antidepressants or antipsychotics, and 10) currently pregnant or trying to become pregnant, or of childbearing potential and unwilling to use a proven method of birth control. Potential participants were required to be off of all antidepressants for a minimum of 2 weeks (6 weeks for fluoxetine) prior to randomization; only 2 participants had been on SSRIs prior to entering the study. Sleep agents (e.g., trazodone < 200 mg; eszopiclone; zolpidem) were allowed as long as the dose had been stable for at least 2 weeks; 14 patients used p.r.n. sleep aids during the study. Participation in a trauma-focused psychotherapy during the trial was prohibited. Participation in other psychotherapeutic modalities maintained for 3 months before and during the trial was permitted; 2 patients were on long-term supportive therapy during the study.

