## STATISTICAL ANALYSIS PLAN

### Statistical Methods

The primary outcome (CAPS-5) was analyzed using an MMRM (mixed model repeated measures) approach based on a modified intent-to-treat (mITT) population, defined as randomized subjects who initiated treatment and had both a baseline and at least one postbaseline outcome score during the blinded phase of the study (Week 10). Participants from the mITT population who were included in the MMRM model also required both a baseline and at least one post-baseline CAPS-5 score. The model included as the dependent variable change from baseline in CAPS-5 total score at each post-baseline visit (Weeks 4, 8 and 10). Independent variables in the MMRM model included treatment, visit, treatment-by-visit interaction, and baseline CAPS-5 total. Visit was treated as a categorical variable. Unstructured variance-covariance structure was used. This same analysis was also repeated on the per protocol population, defined as as all eligible subjects for whom the 10-week assessments for the primary analysis were available and who were dispensed at least 50mg of the protocol prescribed medication at the 6-week time point. Descriptive analyses were performed to compare baseline data between treatment groups. Categorical variables were evaluated using Fisher's exact test. Continuous variables were analyzed with Wilcoxon's rank sum test. Safety data were summarized overall and by treatment groups for the blinded and extended phases of the study. Fisher's exact test was used to compare the number of subjects between groups who experienced any adverse events.

The study was a priori powered assuming 10% attrition and an alpha set to 0.05 using a twosided, two-sample t-test. Based on a sample size of 160 subjects to have an evaluable sample size of 144 (72 per arm), we could detect with 80% power a standardized change score between the groups of 47%. All analyses are based on the modified intent-to-treat (mITT) sample unless otherwise specified.

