Analogous methods to the primary analysis were used for the other continuous secondary outcomes. The categorical secondary outcome, treatment response status, (response defined as a score of 1 ["Much Improved"] or 2 ["Improved"] on the CGI-I) was analyzed using a generalized estimating equation (GEE) model for binary data. The model included the binary responder status at Weeks 1, 2, 4, 6, 8 and 10 as the dependent variable; treatment, visit and the treatment-by-visit interaction as independent variables. Statistical analyses were performed using R version 3.5.2 (http://www.r-project.org).

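### The CGI-I responder GEE leaves out baseline CAPS-5 and the stratification factor site: a valid analysis that may miss a small gain in precision on one secondary outcome

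*Combined protocol and SAP*

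**What the plan says.** Statistical Methods models responder status at six visits, Weeks 1 to 10, with "treatment, visit and the treatment-by-visit interaction as independent variables". That is the whole covariate list; no link function is stated. The primary MMRM has one term more: "treatment, visit, treatment-by-visit interaction, and baseline CAPS-5 total". The only sentence that could carry the baseline term across reads "Analogous methods to the primary analysis were used for the other continuous secondary outcomes", so it stops short of the binary outcome.

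Under Study Design, participants were "randomized in a 1:1 ratio based on a randomly permuted block design stratified by site", and the six sites were "five University academic medical sites and one University active-duty military hospital". Site is in neither the GEE nor the MMRM. Study Assessments places a CAPS-5 interview at Week 0 and lists CGI-I among the key secondary measures.

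**The concern.** The plan treats baseline severity as worth adjusting for in the primary analysis and then drops it for a key secondary outcome, although the score is already collected. If baseline severity predicts response, a Week 10 comparison of response rates is less precise than the data allow.

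Site raises a separate matter. Stratified randomisation balances the arms within site. If response differs between sites, for instance between the military hospital and the academic centres, that balance makes the estimate steadier than a model without site reports. The stated standard error is then somewhat too large and the test slightly conservative. At stake is precision on one secondary outcome; the primary CAPS-5 conclusion is unaffected.

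**Working it through.** **The plan's own figure.** The plan gives an "evaluable sample size of 144 (72 per arm") for 80% power at a standardised difference of 0.47, two-sided alpha 0.05. Per arm, n = 2(1.96 + 0.8416)² / 0.47² = 15.70 / 0.2209 = 71.1, so 72. Noncentral t power with 142 df is 0.800, and 144 / 0.9 = 160. The figure reproduces, but it concerns CAPS-5; none is given for the responder analysis.

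**Assumed inputs, none from the documents.** Control response of 40% at Week 10; a latent treatment shift of 0.47 SD, borrowed from the power statement; rho from 0 to 0.5, where rho is the size of the correlation between baseline CAPS-5 and latent response; and a between-site SD of 0 or 0.3.

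**Unadjusted benchmark.** Treated response = Φ(-0.253 + 0.47) = 58.6%, so the risk difference is 0.186. SE = √[(0.40 × 0.60 + 0.586 × 0.414) / 72] = 0.0819. Power = Φ(0.186 / 0.0819 - 1.96), about 62%.

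**Large-sample gain from baseline alone.** The variance cut is about 0.62 × rho²: 2.5% at rho 0.2, 5.6% at 0.3 and 15.6% at 0.5.

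**Simulation of the six-visit GEE.** Logit link, 144 participants, six sites of 24 balanced by arm, within-person latent correlation 0.7, control response rising from 10% to 40%, 7,000 trials per row. Baseline and five site indicators were added, predictions were standardised over the sample at Week 10, and a small-sample-corrected robust SE was used. There are no site differences in this table.

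| rho | Variance change | Repeat run (8,000) | Power, unadjusted to adjusted |
|---|---|---|---|
| 0 | +0.3% | +0.5% | 62.2% to 60.9% |
| 0.2 | -1.5% | -1.6% | 62.1% to 61.9% |
| 0.3 | -5.1% | -5.0% | 63.2% to 63.4% |
| 0.5 | -16.3% | -17.1% | 63.7% to 69.0% |

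Simulating Week 10 alone gave variance changes of about 0%, -2%, -4% and -13%, and power changes of about -1, 0, +2 and +6 points. With baseline only and an exchangeable working correlation, the change at rho 0.5 was -13.3%.

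**Site differences** (SD 0.3, rho 0.3). The unadjusted reported SE was 0.0817 against an empirical 0.0785, and 0.0817 / 0.0785 = 1.04, so about 4% too large. Power went from 58.3% to 60.5%; simulating Week 10 alone, from 59.9% to 63.0%. In another Week 10 simulation the empirical SD was 0.0804 unadjusted, 0.0781 with baseline, and 0.0781 with baseline and site. Site therefore acts mainly by making the reported SE reflect the stratification.

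**Logit scale.** The SD of the treatment coefficient rises with adjustment: 0.348 to 0.359, 0.346 to 0.370 and 0.347 to 0.394 at rho 0, 0.3 and 0.5.

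**Null rejection** of the adjusted test: 5.0% to 5.1% with the small-sample correction, 5.9% to 6.0% without it.

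**The case against.** The best case for leaving the plan alone is that nothing is wrong with it and the benefit may be nil. CGI-I is itself a rating of improvement, so it already refers to each participant's starting state. The entry rule ("Participants were required to have a CAPS-5 score of" at least 25) also narrows the range of baseline severity. Both make a low rho plausible, and at rho 0.2 or below power does not rise. No passage supports a rho of 0.5. This stands, and it is why the point is minor.

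It is also fair to say that the gain is measured on a quantity the plan does not contain. The documents define no risk difference, no standardisation and no Week 10 contrast for this GEE. A reader might infer that adding covariates would tighten the odds ratio. It would not: under a logit link the coefficient becomes conditional and its SE rises.

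A reader might also convert the variance cut into extra participants. At rho 0.3 that would be 144 × (1 / (1 - 0.051) - 1), or about 8. Eight more participants in the unadjusted test would add about 2 points of power, while the six-visit simulation shows 0.2. The conversion overstates the power gain and should not be used.

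Last, the mITT definition might be read as guaranteeing every participant a baseline CAPS-5. It requires "randomized subjects who initiated treatment and had both a baseline and at least one postbaseline outcome score", without naming the outcome, and the next sentence imposes the CAPS-5 requirement separately for the MMRM. A few participants could therefore lack it.

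None of this alters the fact that a collected covariate and the stratification factor are left out.

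**Conclusion.** The point holds as a minor efficiency suggestion for one secondary outcome. A reader might infer from the missing covariates that the responder analysis is biased or invalid. The documents do not support that: randomisation protects the unadjusted marginal comparison, and leaving out site makes it at worst slightly conservative.

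Under the assumptions above, adjustment reduces the variance of a standardised Week 10 risk difference by between nothing (rho 0) and 13% to 17% (rho 0.5). The power change runs from about -1 point to +5 or +6, and is 0 to +2 at rho 0.3. If sites differ with SD 0.3 and rho is 0.3, power rises by about 2 to 3 points. These sizes rest on an assumed response rate, effect, rho and site variation; the omissions themselves are plain from the text.

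**What to change.** Keep the planned GEE and report it as written. Beside it, labelled as added, fit the same model with baseline CAPS-5 total and site, pooling very small sites. Report the Week 10 effect as a standardised marginal risk difference with a bootstrap or small-sample-corrected robust 95% confidence interval. Fill any missing baseline CAPS-5 with the overall mean so that no mITT participant is lost.

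The cost is modest programming on data already collected. If neither covariate predicts response, about 1 point of power is lost on the added analysis. The small-sample correction (or the bootstrap) is needed to avoid the near-6% null rejection shown above. Because the plan is written in the past tense, the adjusted result can only supplement the planned one and should not replace it.
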